4.1 Objectives

The study objectives are to:

- Understand the intervention mechanisms that contribute most to these outcomes and why.
- Focus on the impact on younger people and middle-aged adults.
- Assess the association between L2 DBI intervention and unscheduled health care use.

- Elicit the health care, social care and third sector resource use over a 12-month period for people who receive a L2 DBI.
- Identify care pathways used by GPs to support people in distress with suicidal ideation, behaviour or self-harm and estimate associated resource use.
- Produce learning in a format that will inform the continued improvement of DBI and the wider service system.

4.2 Outcome

Key study outcomes include suicidal ideation, suicidal behaviour, self-harm reduction in the immediate (1 month), short (3-4 months) and longer term (1 year).

Secondary outcome measures are improved resilience, self-stigma, mental and physical health in the immediate (1 month), short (3-4 months) and longer term (1 year) and service usage one month and one year prior to and following DBI.

5 STUDY DESIGN and METHODS of DATA COLLECTION AND DATA ANALYIS

5.1 Study design

This is a mixed method evaluation with continuous improvement elements. The design chosen is pragmatic and has the advantage of providing the nuanced understanding required to produce findings with real-world application as intended. Recent evidence suggests that for those using mental health crisis services, what matters to them is that outcomes are measured on a more individual than general level and there is an emerging argument for developing more innovative approaches to studying outcomes in mental health/crisis₂₃.

Understanding and achieving value in services for people with mental health problems must consider what outcomes matter for those who use services; currently there is no clear consensus between service providers and users on which outcomes really matter in mental health services. Whilst traditional clinical outcome measures help understanding of outcomes at scale, they rarely consider individual life circumstances, the therapeutic value of the connection between service user and provider, compassion, stigma, or basic alleviation of distress²⁴. The DBI service is accessed by people from diverse backgrounds with an array of problems that are individual to them and DBI is designed to be tailored to the individual. Therefore, to understand the extent and nature of the impact of DBI on suicidal thoughts, behaviour and self-harm this study will incorporate a combination of quantitative and qualitative measures of outcomes attributable to DBI that capture clinical, therapeutic relationship and individual personal experience and directly informed by PPI.

The original DBI pilot evaluation₁₂ has shown the feasibility and acceptability of involving DBI providers and those who use the DBI service in evaluation (800+ service user pre and post surveys, 20 service user interviews, 57 staff involved in interviews and focus groups). The study team are experienced in conducting data linkage studies using Public Health Scotland's Unscheduled Care Datamart 24,25,26.

The DBI programme has a standardised routine data system supported by a Public Health Scotland based information analyst [name], [name] will be a joint applicant in the Public Benefits and Privacy Panel application for data linkage and facilitate access to DBI routine datasets held by Public Health Scotland. [name] (Associate Medical Director NHS 24) will facilitate access to NHS24 data to identify individual patient records for

the comparator group analysis.

5.2 Data Collection

5.2.1 Quantitative surveys for individuals accessing DBI:

Individuals accessing DBI who provide informed consent will be invited to complete a L2 DBI service users survey at their first and final DBI L2 sessions for baseline and immediate outcome data (approximately two weeks apart). These surveys will be administered by DBI L2 staff as described in section 7.1. The surveys are largely quantitative and include a combination of validated scales and bespoke closed questions as well as a small number of open questions to measure the following:

- Impact of assurance of contact 24 hours from referral.
- Level of distress₂₇, suicidal ideation, suicidal behaviour and self-harm₂₈, identifying first time/repeat disclosure
- Feelings of entrapment/hopelessness/despair₂₉
- Resilience 30
- Self-stigma₃₁
- Health related quality of life 32
- Perceptions of the DBI aspects, if any, that are most beneficial for above outcomes
- Impact of other different sources of support or life circumstances on the above outcomes
- Health, social care and third sector resource use
- Smart phone and/or email and/or postal address to enable ScotCen research team to administer the 3 month follow-up and 1 year follow-up surveys electronically or address for postal.

Equality and diversity questions are not included in the surveys because demographic data will be linked to survey responses from routine DBI service data for those who consent; this will also help to reduce burden on participants.

At the end of DBI support, participating individuals will be emailed, text, handed in person or posted their second survey by the L2 DBI team.

- Surveys will take 15-20 minutes to complete and can be completed on paper or online and if requested translated versions will be supplied.
- An incentive of £10 will be distributed on completion of each the 4 surveys.
- For paper surveys, L2 staff will write the DIMES study unique identifier onto the paper survey before administering it.
- For online surveys, in their introductory email, individuals will be supplied with their unique DIMES study identifier to use to access their online survey.

Follow-up L2 DBI service users survey for individuals accessing DBI – at 3-4 months and 1 year following the start of the DBI intervention

Using the contact details provided by participants in their consent form and/or their second survey, online or paper surveys will be sent by the ScotCen research team to all evaluation participants at 3-4 months and 1 year following their final DBI session to capture any on-going impact of DBI. In addition to repeating the scales collected in the initial surveys, the follow-up surveys seek to measure help-seeking behaviour improvement, other positive outcomes related to DBI presenting problems/life circumstances e.g. physical health, relationships, addictions, financial, and ask whether further support from DBI would be beneficial, what form this might take and why. Two brief reminders will be sent for each of the follow-up surveys (supporting documents 19 and 20).

A £10 thank you voucher will be provided to participants on completion of each of the four surveys above.

5.2.2 Linkage of individual level DBI L2 individual survey data with routine DBI data

Individual level data linkage between the DIMES participant survey dataset and DBI routine dataset will be undertaken for all evaluation participants who give their consent. This will enable the study team to link outcome data with service user characteristics and DBI intervention activity to facilitate analysis of service user sub-groups and intervention factors such as number of sessions, intervention length and onward referral.

Public Health Scotland (PHS) hold the DBI routine dataset. The linkage will be facilitated by ScotCen supported by [name] who is responsible for managing the DBI routine datasets at PHS. The linked dataset will be stored securely in the Safe Haven for the study team to access remotely. ScotCen would securely transfer the DIMES participant survey dataset to PHS via Secure File Transfer Protocol with the DIMES study unique identifier to enable linkage of the survey data to the DBI routine dataset (which also includes the DIMES study unique identifier).

We will also link the above combined dataset to the Unscheduled Care Datamart (UCD) to examine differences in unscheduled care use one year before and after DBI.

Permission to undertake this linkage will be sought from the Public Benefits and Privacy Panel.

5.2.3 Qualitative interviews with individuals accessing DBI

Qualitative interviews with evaluation participants will be undertaken at 1 month, 3-4 months and 1 year following DBI L2 intervention. These in-depth face to face, video or telephone interviews will take place with evaluation participants who have agreed in their second survey (issued at their final DBI L2 session) to be contacted for interview, who have experienced suicidal thoughts, behaviour or self-harm on referral to DBI L2 and who have been assessed as eligible during the Safe Screening process outlined in section 7.3. The study team researchers undertaking the interviews will be ASIST (suicide prevention) trained. It is planned that up to six attempts will be made to contact those who have agreed to participate in interviews, however this will be reviewed with the Study Advisory Group.

The qualitative interviews will last for approximately one hour and will be semi-structured and focus on:

- The individual's DBI story from referral to exit from DBI and ongoing impact of the DBI intervention
- Perceptions of what aspects of DBI support, if any, were most beneficial in helping with studyspecific outcomes (suicidal ideation, suicidal behaviour and self-harm, self-stigma and resilience) as well as contributory outcomes e.g. financial support
- Impact of other sources on above outcomes (life circumstances, informal support, support from follow-up services that DBI sign-posted to and any other formal sources of support)
- Unintended consequences of the DBI intervention
- Differences in experiences of other services accessed in distress/ suicidality/self-harm
- Perceptions of whether and how support from DBI at the 3-4 month and/or year stage would be beneficial
- Impact of Covid-19 on own distress/suicidality
- Ways in which DBI could be improved

Participants will receive a £25 thank you voucher for their time following each interview.

5.2.4 Comparator group data collection

An RCT study design is not possible for this study. In the Scottish Government's Evaluability Assessment of the DBI Programme₃₄ a control trial was assessed as an option for the evaluation of the effectiveness of DBI and several major challenges to this were identified. The difficulty in obtaining a control group has been compounded by the national roll-out of DBI L1 in May 2020 whereby all adults in Scotland, if assessed appropriate by NHS24, can now access DBI by phone. From mid-May 2020 to 25th May 2021 there were 3225 NHS24 referrals to DBI Level 2. In the 8-week period up to the 25th May 2021, there were 655 NHS 24 referrals, an average of 82 per week. This national rollout of DBI via NHS24 has made direct comparison against usual care in different regions of Scotland unfeasible. We cannot use other UK or European countries as a control due to the different health, social care and police service systems and policies. Any comparisons with higher level English/UK data would be very difficult to relate any observed differences to DBI. Additionally, other voluntary sector routes for people in distress such as the Samaritans cannot be used as a control as they operate anonymously.

Given the above, we will identify a retrospective comparator group to undertake a comparison with the DBI service user group above using available national data. There are no nationally available standardised outcomes data for people who present to frontline services that are referral routes to DBI (e.g. police, primary care, A&E) in distress. The Scottish Suicide Information database (ScotSID) only has information on those who have probably died from suicide thus numbers would not be sufficient. ScotSID is part of the Unscheduled Care Datamart (UCD) which links data from NHS24, Scottish Ambulance Service, Out of Hours Primary Care, Emergency Department, Acute and Mental Health services and deaths. Given the limitations set out above, the UCD is the most appropriate place to obtain a comparator group.

Since the inclusion of NHS24 as a Level 1 DBI provider in May 2020, it has become the main referral agency. We will select the comparator group from those accessing NHS24 who were not referred to DBI because they accessed services prior to its roll out throughout Scotland via NHS24. We will request Unscheduled Care Datamart (UCD) records, which links data from NHS24, Scottish Ambulance Service, Out of Hours Primary Care, Emergency Department, Acute and Mental Health services and deaths, for 2018-2019 for people who contacted NHS 24 in October 2019 to March 2020 for mental health reasons. The NHS24 data indicates whether a call went to the Mental Health Hub (MHH). NHS24 receives around 130,000 calls a month and around 3% of these are related to mental health₃₄. We will use a call related to mental health as the comparator event and collect information on service use outcomes in the year before and the year after the index call. The comparator event(s) is/are a good proxy for presenting to unscheduled care experiencing mental distress as measured by the distress thermometer used by Level 1 services to assess for referral to DBI. People who received DBI intervention during the same period will be identified through the DBI database held by Public Health Scotland which will be linked to the UCD by eDRIS.

We will also collect demographic information on these individuals e.g. age, gender, ethnicity, SIMD, geographic region, rates of previous unscheduled care use and presence of physical co-morbidity. We will use doubly robust estimation which combines a regression model of the outcome with a model for the exposure (ie the propensity score) to estimate the effect of an exposure on an outcome₃₅.

The use of unscheduled care in the year before and after the selected year for the comparator group and the data collection year for DBI service users will be compared to assess whether use of unscheduled care in the year after is lower for DBI service users. We will also collect data on the primary and (where available) secondary presenting problems as described by each unscheduled care service on the UCD for comparison. The presenting problem descriptors differ across the services. Where listed our analysis will include, but not be limited to:

- Mental health problems
- Self-harm

- Attempted suicide
- And completed suicide

The above comparative analysis will not compare contextually like for like scenarios but will have value as an approximation of the impact of DBI on future use of unscheduled care. We would expect unscheduled care use to be lower in the year after the index event than in the year before due to regression to the mean. If DBI L2 reduces emotional distress and increases capacity for self-management then we would expect the reduction in unscheduled care use (particularly for mental health, self-harm, suicide attempt and completed suicide) to be greater for those receiving DBI intervention than in the historical comparator group. In addition, we will compare, within people who are referred to DBI, whether changes in unscheduled care use are different for those referred for reasons of suicidality or self-harm compared to those who are not.

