1 BACKGROUND

Suicide presents a significant challenge across the UK. In 2018₁ there were 784 deaths by suicide in Scotland. Scotland has consistently had the highest recorded UK suicide rate since the 1990's. Nearly 1 in 2 people (44.2%) who died by suicide were in contact with at least one unscheduled care service in the year before death. They were more likely to have had this contact than the general public₂ who did not die by suicide. Nearly three-quarters (73%) had contact with at least one health service in the year prior to death. In Scotland, suicide attempts are most prevalent amongst young (16-24) and middle-aged adults, although men and women in middle-age are most likely to die by suicide₃; almost half are aged 35-544. Younger adults are most likely to self-harm and experience isolation₅. Self-harm and suicidal ideation are strongly associated with a lifetime risk of suicide₆. A common driver for all the above is mental distress. Against a background of deteriorating mental health among young people pre-Covid-19, recent evidence suggests that mental distress has increased in the UK population under Covid-19, particularly amongst young adults, women, those employed pre-pandemic and those living with children_{7,8}.

Distress Brief Interventions Programme

To address the need to improve the response to adults (aged 18+) in distress highlighted by the Scottish Government (SG) Suicide Prevention₉ and Mental Health strategies₁₀, the Scottish Government (SG) developed the Distress Brief Intervention (DBI). The DBI was developed and delivered by the University of Glasgow (led by co-applicants RO and JMel) from a literature review₁₁, and consultations with service users and stakeholders. Distress is defined by DBI as '*An emotional pain for which the person sought, or was referred for, help and which does not require (further) emergency service response*'. The DBI pilot programme was launched in 2017.

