5.3 Data analysis

Survey data analysis will include descriptive statistics and crosstabulation analysis with logistic regression if appropriate. We will compare demographic, referral source and presenting problem characteristics of survey respondents and non-respondents to assess the representativeness of the survey sample and whether any weighting adjustments are required.

Qualitative survey data will be coded using a staged content approach. Qualitative interviews will be summarised, charted and coded using QSR NVivo 12 and analysed with reference to techniques of framework analysis. Focus groups will be analysed using a framework matrix to explore themes across the data₃₇. We will explore any differences or similarities in the views of the DBI and control qualitative participants to assess any perceived impact of the DBI intervention, while paying attention to other contextual influences.

The data linkage analysis will assess whether the difference in frequency of unscheduled care in the year post intervention differs between DBI participants and the comparator group by doubly robust estimation₃₄ adjusted for unscheduled care received in the preceding year. This analysis will include adjustment for potentially confounding sociodemographic variables. Secondary analyses and likely zero inflation will be assessed. A full Statistical Analysis Plan will be developed prior to the identification of the comparator group. For the health economic analysis, units of each item for all care pathways and for participant resource use will be collated and presented along with unit costs which will be derived from local sources as well as those which are publicly available₃₈.

A summative data synthesis will be undertaken to draw together the above through a process of triangulation to develop evidence-based insights and conclusions. Throughout the study, the study team and the SAG, will meet to share thematic and theoretical insights from data collection and analysis and develop interpretive connections and points of synthesis. Policy and practice recommendations will be made.

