For the comparator group quantitative analysis the sample size is based on 2500 people accessing the DBI L2 during the study period. Assuming the model: generalised linear model using binomial family and a logit link with dependent variable 'UCD use in the year after' and independent variables 'UCD use in the preceding year' and 'group' (DBI versus comparator). Estimating the following odds ratios for the model: intercept 0.80, group 0.70, UCD use in preceding year 2.0 and assuming the DBI group represents 10% of the total analysis sample and that the probability of UCD use in the preceding year is about 70% (estimate based on evaluation data) with alpha set to 0.05 we would have over 90% power to test that the odds ratio for 'group' is different to 1.

NHS 24 MHH qualitative interviews: 15. The sample of 15 interviews is based on the premise that the open invitation to participate through mental health lived experience networks will yield small numbers, however 15 interviews should be sufficient to provide the insights required for this study.

Stakeholder focus groups: 42 – 56 (6-8 per focus group). It is intended to hold one focus group per site. Given the relatively standardised nature of DBI it will not be necessary to hold multiple focus groups per site. 6-8 participants is a standard and recommended amount of people per focus group to aid discussion.

GP survey: 20. This should be sufficient to enable the generation of stylised pathways that are reflective of current practice. Recruitment of GPs to studies is very difficult due to their limited time so we would not wish to unnecessarily invite higher numbers to participate to minimise burden.

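### Contacts arising from the index NHS24 call can count as outcome in the comparator more often than in the DBI group, which biases the unscheduled-care comparison towards DBI

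*Protocol*

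**What the plan says.** - **Comparator index and window.** Section 5.2.4 takes a mental-health call to NHS24 as the index: "We will use a call related to mental health as the comparator event and collect information on service use outcomes in the year before and" after that call.
- **Outcome source.** The same section draws on a national linked dataset, the UCD (Unscheduled Care Datamart), described there as one "which links data from NHS24, Scottish Ambulance Service, Out of Hours Primary Care, Emergency Department, Acute and Mental Health services and deaths".
- **DBI window.** Section 5.3 asks "whether the difference in frequency of unscheduled care in the year post intervention differs between DBI participants and the comparator group", with adjustment for use in the preceding year. Section 5.2.2 likewise looks at one year before and after DBI. Under section 1, the Level 1 presentation comes first and Level 2 makes contact within 24 hours of it.
- **Who can be in each group.** Section 1 defines DBI distress as distress for which help was sought "which does not require (further) emergency service response". The comparator criteria in sections 5.2.4 and 7.1 ask only for an NHS24 contact for mental health reasons between October 2019 and March 2020.
- **A second window.** Later in section 5.2.4, use is to be compared in the years on either side of a selected year (comparator) and of the data collection year (DBI). That is not a window around each person's index call.
- **Outcome measure.** Section 5.3 speaks of frequency. Section 7.2.1 models any UCD use in the year after, with a "generalised linear model using binomial family and a logit link". Neither defines what is counted.

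**The concern.** The outcome source covers services to which an NHS24 call can lead. If a comparator's call is followed the same day by an ambulance, an emergency department visit or an admission, those records fall after the index call and so inside the outcome year. They belong to the crisis that selected the person, not to what happened afterwards.

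The DBI group is placed differently in two ways. Its clock starts at the intervention, so the contacts that made up the presentation fall before it; where they enter the prior-year count, they add to the apparent fall in use. Its members are also people judged to need no further emergency response. Both differences push the same way.

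The planned adjustments do not reach this. Prior-year use is measured before the index and the onward contacts fall after it. The covariates listed in section 5.2.4 describe demographics, previous use and physical co-morbidity, not how the index call ended. Section 5.2.4 says a greater reduction in the DBI group is what would be expected if DBI works, and this artefact produces the same pattern. At stake is the protocol's only individual-level quantitative comparison with people who did not receive DBI.

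**Working it through.** **Inputs from section 7.2.1:** intercept odds 0.80, group odds ratio (OR) 0.70, prior-use OR 2.0, prior use 70%, DBI 10% of the sample, 2500 DBI users, alpha 0.05.

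**Input not in the documents:** the share f of comparators whose index call produces an onward UCD contact. A range is used.

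**1. The plan's own figures.**
- Comparator probability of any use: p = 0.3 × (0.80/1.80) + 0.7 × (1.60/2.60) = 0.133 + 0.431 = 0.564, odds 1.294.
- DBI probability under the design OR: 0.3 × (0.56/1.56) + 0.7 × (1.12/2.12) = 0.478.
- With 2500 DBI users and 22,500 comparators (10% to 90%), Wald power for the group term exceeds 99.9%. This agrees with the stated power of over 90%.

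**2. No true effect, onward contacts in the comparator only.** Observed comparator probability p' = p + (1 − p)f. Apparent OR = 1.294 / [p'/(1 − p')].

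| f | p' | odds | apparent OR | same, adjusted for prior use |
|---|---|---|---|---|
| 10% | 0.608 | 1.549 | 0.84 | 0.83 |
| 20% | 0.651 | 1.868 | 0.69 | 0.69 |
| 30% | 0.695 | 2.277 | 0.57 | 0.56 |

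The last column fits the section 7.2.1 model (group and prior use) to the expected data. Adjustment leaves the bias in place. Under these assumptions f of about 19% gives 0.70.

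**3. DBI users have half the comparator's onward rate.**
- f = 10%: DBI probability 0.564 + 0.436 × 0.05 = 0.586, odds 1.415; OR = 1.415/1.549 = 0.91.
- f = 20%: DBI odds 1.549; OR = 1.549/1.868 = 0.83.
- Equal rates in both groups give 1.00.

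**4. Onward contact concentrated in people who would use services later anyway.** Step 2 assumes the two are independent. Suppose instead that 80% of those with an onward contact would have had later use regardless. Then p' = p + 0.2f. At f = 20%, p' = 0.604, odds 1.526, OR = 0.85. Reaching 0.70 needs p' = 0.649, so f = (0.649 − 0.564)/0.2, or about 42%.

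**5. Consequence for the test.** Under step 2 with 2500 against 22,500, the chance of a significant result with no effect is about 57% at f = 5% and 99% at f = 10%. With 250 against 2250 it is about 10% and 27%. A large sample makes a small bias look conclusive.

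**6. Which window.** The individual window around the index or intervention appears at the comparator definition in section 5.2.4, again in that section's discussion of regression to the mean, and in sections 5.2.2 and 5.3. The selected-year window appears once. Read literally, that one would put same-day onward contacts inside the selected year and outside the outcome year, and the mechanism would largely disappear.

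**The case against.** Four points on the other side have force.

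- **Counting unit.** A reader might infer that the plan counts service records rather than crisis episodes. The document does not say so; the unit is undefined, and a statistical analysis plan, which section 5.3 promises before the comparator is identified, could properly define it. The odds ratios above do not depend on it, because they use a yes/no outcome that a single onward contact turns to yes. What the protocol itself fixes is the index, the window and the unrestricted comparator, and those create the imbalance.
- **DBI users and onward contacts.** A reader might also infer that DBI users can have no such contacts. The definition rules out a further emergency service response, not every UCD contact; out-of-hours primary care is one example. Step 3 is therefore needed alongside step 2.
- **The 20% figure.** It is tempting to say that an onward share of about 20% explains the whole design effect. That holds only if DBI users have none and onward contact is independent of later use. The documents give neither the share nor those conditions.
- **Standing of the comparison.** Section 4.2 lists service use as secondary, and section 5.2.4 concedes that the comparison is not like for like and is an approximation. The caveat is general: it names regression to the mean but not this mechanism, and gives a reader no way to see that the error has a known direction.

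**Conclusion.** The concern holds in this form: followed as written, the comparator's window lets index-episode contacts into the outcome more often than the DBI group's does. The direction favours DBI, and adjustment for prior-year use does not correct it. Two ambiguities make it worse: section 5.2.4 gives two incompatible windows, and sections 5.3 and 7.2.1 leave the counted unit open.

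The size is not known. For shares of 10% to 30%, the apparent OR with no true effect runs from about 0.84 to 0.57 in the worst case. It is about 0.91 at 10% and 0.83 at 20% if DBI users have half the comparator's rate, and moves closer to 1 if those with onward contacts would mostly have had later use anyway. These figures rest on the section 7.2.1 inputs and an assumed onward share. They show that the bias can be of the same order as the effect sought, not that it will be.

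**What to change.** In sections 5.2.4 and 5.3:

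1. Replace the two windows with one, defined for each person.
2. Anchor both groups at the equivalent presentation contact (the NHS24 call for comparators, the Level 1 presentation for DBI users).
3. Define the index episode as the records chained to that contact within a short gap fixed in advance, including any resulting hospital stay. Exclude all of it from both the prior-year and the outcome counts, by the same rule in both groups, and start follow-up at its end.
4. State the unit of the outcome, and use it consistently in sections 5.3 and 7.2.1.
5. Report as sensitivity analyses the result without the exclusion and with other gap lengths.
6. As far as the UCD allows, add a sensitivity analysis restricted to comparators whose index call led to no emergency response. Excluding the episode does not by itself remove that difference in case mix.

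The cost is protocol wording and data-preparation code in the Safe Haven. No new data source is needed if contact dates and times are requested, so this should be settled before the linkage application described in section 8.2. The drawback is that a genuine new contact within the gap is merged into the index episode; the alternative gap lengths show how much that matters.
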